9.2 Sample Size/Accrual Rate

With this classical 3+3 design, there is no statistical testing, rather a variety of dose-escalation strategies will be employed to target a DLT rate of <33%. Applying this design to the 5 dose levels (-1, 1, 2, 3 and 4), starting with dose level 1 (as indicated in Table 1 in Section 6), the total number of patients evaluable for DLT ranges from 3 to 24. Assuming an average of 4 or 5 patients per dose level (some may require 3, other 6), approximately 18 patients can be anticipated. Accounting for approximately 20% of patients subsequently found to not be evaluable for DLT, enrollment of 23 patients is expected in Part A (3+3 phase), with a maximum of 30.

During the expansion cohort for dose/schedule refinement (Iasonos and O’Quigley, 2016), an additional 15 patients (factoring in the 20% DLT inevaluability as well) will be treated at MTD, leading to a maximum sample size of 45, with a likely size between 35-42

Stopping rule: The 3+3 is a straightforward algorithmic design, where development of DLTs in more than 1 of 6 subjects in a specific dose cohort suggests that the MTD has been exceeded, and further dose escalation is not pursued. So here, the stopping rule is to repeat until MTD is achieved, or the trial is stopped.

PLANNED ENROLLMENT REPORT

Racial Categories	Ethnic Categories				Total
	Not Hispanic or Latino		Hispanic or Latino		
	Female	Male	Female	Male	
American Indian/ Alaska Native	0	0	0	0	0
Asian	0	0	0	0	0
Native Hawaiian or Other Pacific Islander	0	0	0	0	0
Black or African American	7	6	0	0	13

Racial Categories	Ethnic Categories				Total
	Not Hispanic or Latino		Hispanic or Latino		
	Female	Male	Female	Male	
White	16	14	1	1	32
More Than One Race	0	0	0	0	0
Total	23	20	1	1	45

PHS 398 / PHS 2590 (Rev. 08/12 Approved Through 8/31/2015)

OMB No. 0925-0001/0002

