6. TREATMENT PLAN

6.1 Agent Administration

This will be a two-part phase 1 dose-escalation and exploratory dose-expansion study of MLN4924 (pevonedistat) in combination with belinostat. Part A will consist of a 3+3 dose-escalation phase of the combination to assess its safety and tolerability and identify an MTD/tentative RP2D. After the MTD has been established, Part B of the study will involve an exploratory-dose expansion study of 12 additional patients who will be enrolled at the tentative RP2D to gain further insights into the safety of the regimen. MLN4929 (pevonedistat) and belinostat dose rounding is allowed per institutional guidelines.

Treatment will be administered on an outpatient basis. Cycles are to be repeated every 21 days. Reported adverse events and potential risks are described in Section 10. Appropriate dose modifications are described in Section 7. Other than hydroxyurea during the first 5 days of study treatment, no investigational or commercial agents or therapies other than those described below may be administered with the intent to treat the patient's malignancy.

Dose Escalation Schedule				
Dose Level	Belinostat		MLN4924 (pevonedistat)	
	Dose (mg/m²/day)	Administration and Schedule	Dose (mg/m²/day)	Administration and Schedule
-1	800	Intravenously over 30 minutes once daily on Days 1-5 of each 21-day cycle	15	Intravenously over 60 minutes once daily on Days 1, 3, & 5 of each 21-day cycle**
1*	800		20	
2	800		25	
3	800		37	
4	1000		37	
5	1000		50	
6***	1000		59	

* Starting dose level

** When both drugs are given on the same day (Days 1, 3, 5), start the MLN4924 (pevonedistat) infusion within 60 mins after the completion of belinostat infusion.

*** The 59 mg/m² level will not begin until the NCI/CTEP, Principal Investigator and Takeda have closely examined the toxicity, PK and clinical data from the 50 mg/m² cohort. Takeda must give written approval for the 59 mg/m² to begin.

Regimen Description				
Agent	Premedication; Precautions	Dose And Route	Schedule	Cycle Length
Belinostat	See Section 6.4	In 250 mL 0.9% NaCl IV over 30 (± 5 min)*** Dose per assigned dose level.	Days 1-5 (week 1)	21 days (3 weeks)
MLN4924 (pevonedistat)	See Section 6.4	In 250 mL D5W or 0.9% NS IV over 60 min (± 10 min)* Infusion to start within 60 minutes after belinostat infusion ends. Dose per assigned dose level.	Days 1, 3, & 5 (week 1)**	

IV = Intravenously; D5W = dextrose 5% in water; NS = normal saline.

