7. DOSING DELAYS/DOSE MODIFICATIONS

7.1 Dose Reduction Steps

Belinostat Dose-Reduction Steps*	If starting dose of belinostat is:	
	800 mg/m ²	1000 mg/m ²
-1	600 mg/m ² (Days 1-5)	800 mg/m ² (Days 1-5)
-2	Discontinue	600 mg/m ² (Days 1-5)
-3	-	Discontinue

* At the discretion of the investigator, if toxicity has resolved following a required dose reduction, the dose may be escalated, but not to levels higher than the patient's initial dose level and **not during Cycle 1**.

MLN4924 (pevonedistat) Dose- Reduction Steps*	If starting dose of MLN4924 (pevonedistat) is:					
	15 mg/m ²	20 mg/m ²	25 mg/m ²	37 mg/m ²	50 mg/m ²	59 mg/m ²
-1	Discontinue	15 mg/m ² (Days 1, 3, 5)	20 mg/m ² (Days 1, 3, 5)	25 mg/m ² (Days 1, 3, 5)	37 mg/m ² (Days 1, 3, 5)	50 mg/m ² (Days 1, 3, 5)
-2	-	Discontinue	15 mg/m ² (Days 1, 3, 5)	20 mg/m ² (Days 1, 3, 5)	25 mg/m ² (Days 1, 3, 5)	37 mg/m ² (Days 1, 3, 5)
-3	-	-	Discontinue	15 mg/m ² (Days 1, 3, 5)	20 mg/m ² (Days 1, 3, 5)	25 mg/m ² (Days 1, 3, 5)
-4	-	-	-	Discontinue	15 mg/m ² (Days 1, 3, 5)	20 mg/m ² (Days 1, 3, 5)
-5	-	-	-	-	Discontinue	15 mg/m ² (Days 1, 3, 5)
-6	-	-	-	-	-	Discontinue

* At the discretion of the investigator, if toxicity has resolved following a required dose reduction, the dose may be escalated, but not to levels higher than the patient's initial dose level and **not during Cycle 1.**

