9. STATISTICAL CONSIDERATIONS

9.1 Study Design/Endpoints

This study will be a phase 1 trial of MLN4924 (pevonedistat) and belinostat in relapsed/refractory acute myeloid leukemia or myelodysplastic syndrome employing a “3+3” dose escalation strategy applied to 4 dose levels, with provision for 1 level of dose reduction. Additional patients will be enrolled at the MTD until a total of 12 patients have been treated at the MTD.

Primary endpoint

- RP2D for the combination of MLN4924 (pevonedistat) and belinostat in the study population.

Secondary endpoints

- AEs using NCI CTCAE v5.0.

- Treatment responses classified according to International Working Group (IWG) and European Leukemia Net (ELN) criteria for response assessment in AML and MDS. Duration of response defined as the time from documentation of tumor response to disease progression or death, whichever occurs first. Time to response defined as the time from registration to the time of documentation of tumor response.
- [REDACTED]
- MLN4924 (pevonedistat) and belinostat plasma concentrations measured at baseline (pre-treatment) and at defined time points in Cycle 1.
- Candidate biomarker levels in bone marrow and/or blood samples pre- and 24-hr post-treatment with the first doses of study drugs (e.g., p-Wee1, p-cdc2 and γ -H2A.X).

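### Sections 9.1 and 9.2 size the trial for four escalation levels (24 evaluable, 30 in Part A, 45 overall), but the schema, 6.1 and 7.1 provide for six, the sixth conditional; 9.2's own arithmetic then gives 30/38/53 or 36/45/60

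*Combined protocol and SAP*

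**What the plan says.** **Statistical section.** 9.1 describes a 3+3 escalation "applied to 4 dose levels, with provision for 1 level of dose reduction". 9.2 works from "Applying this design to the 5 dose levels (-1, 1, 2, 3 and 4), starting with dose level 1" and refers to the table in Section 6 for those levels. It then states that "the total number of patients evaluable for DLT ranges from 3 to 24", that "enrollment of 23 patients is expected in Part A (3+3 phase), with a maximum of 30", and, after adding 15 expansion patients, reaches a figure "leading to a maximum sample size of 45, with a likely size between 35-42". The planned enrolment table totals 45.

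**Treatment sections.** The dose table in the schema and in 6.1 lists levels -1 and 1 to 6. The footnote to level 6 says that this "level will not begin until the NCI/CTEP, Principal Investigator and Takeda have closely examined the toxicity, PK and clinical data from the" patients treated one level below. It sets a further condition, "Takeda must give written approval for the 59", which is the pevonedistat dose of level 6. Level 5 carries no such footnote. It needs only the principal-investigator sign-off that 13.1 requires for every escalation decision. The pevonedistat table in 7.1, headed "If starting dose of MLN4924 (pevonedistat) is", has columns for 50 and 59 mg/m², the doses of levels 5 and 6.

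**Part B.** 9.1 adds patients until 12 in all have been treated at the MTD. 6.1 and 6.4 enrol 12 more on top of Part A. The DLT trigger in 6.4 is written for 12 expansion patients, and 9.2 adds 15 to allow for inevaluability. 6.3 requires at least 6 patients at the RP2D.

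**The concern.** The section that fixes the trial's size counts two fewer escalation levels than the section that governs treatment, although it cites that section's table as its source. No passage stops escalation at level 4, and none gives a sample size for levels 5 and 6. Both statements are current text with all figures visible, so redaction does not explain the difference.

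At stake is accrual planning. If escalation proceeds as the dose table allows, the stated maximum and the enrolment table can be passed, which would call for an accrual amendment or a shorter Part B. The two descriptions of Part B add to the problem, because the expansion could be half the size that the 6.4 trigger assumes.

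**Working it through.** **Inputs.** Up to 6 patients per level (6.3 and 9.2); an average of 4 or 5 per level (9.2); 20% not evaluable for DLT (9.2); 12 additional expansion patients (6.1, 6.4). Enrolment = evaluable/0.8, rounded up. Expansion = 12/0.8 = 15.

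**Reproducing 9.2 with four levels.** Maximum: 4 × 6 = 24; 24/0.8 = 30; 30 + 15 = 45. Expected: 4 × 4.5 = 18; 18/0.8 = 22.5, so 23. All match the plan. The sums are right for the level count used; the level count is what differs.

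**Same method, levels in the dose table.**

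| Levels | Maximum evaluable | Part A | Overall | Expected evaluable (4.5 per level) | Part A | Overall |
|---|---|---|---|---|---|---|
| 1-4 | 24 | 30 | 45 | 18 | 23 | 38 |
| 1-5 | 30 | 38 | 53 | 22.5 | 29 | 44 |
| 1-6 | 36 | 45 | 60 | 27 | 34 | 49 |

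The stated overall maximum is 53 - 45 = 8 short for five levels and 60 - 45 = 15 short for six. With six levels, the Part A maximum alone equals 45. The expected columns apply only if every listed level opens.

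**Without any DLT rate.** Take six levels, 3 patients at each of levels 1 to 5 and 6 at level 6:

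- No lower cohort expanded: 15 + 6 = 21; 21/0.8 = 26.25, so 27; total 42.
- One lower cohort expanded: 24; 30; total 45.
- Two lower cohorts expanded: 27; 33.75, so 34; total 49.

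With five levels and 6 patients at level 5, the unexpanded run is 18, 23 and 38. It takes three expanded lower cohorts to pass 45 (27, 34, 49).

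**How far these are bounds.** They are upward-path figures. If escalation stops at the top level and steps down through levels first treated with 3 patients, and then through level -1, up to 6 further evaluable patients are added. The results are 30/38/53 for four levels, 36/45/60 for five and 42/53/68 for six. In addition, 6.3 sets 3 as the least number to add when a cohort is expanded, and dividing by 0.8 is an average inflation.

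**Chance of passing 45 (illustrative).** The documents give no DLT rates for the combination, so four sets were assumed, linear over levels 1 to 6: 3-20%, flat 10%, 5-33% and 10-50%. Shorter runs use the first four or five rates. Level -1 takes the level 1 rate, the top level and any de-escalated level are filled to 6, and Part B is omitted if there is no MTD. Exact enumeration of the 6.3 rules with fixed 20% inflation gives, in that order:

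- six levels: 17.1%, 17.6%, 12.7%, 3.9%
- five levels: 1.5%, 2.2%, 2.5%, 1.9%
- four levels: 0.00% in each set.

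**Part B.** With at least 6 already at the RP2D, the 9.1 wording adds at most 12 - 6 = 6, against 12 in 6.1 and 6.4. Since 12/0.8 = 15, 9.2 agrees with 6.1 and 6.4, and 9.1 stands alone. On the 9.1 reading, the overall upward-path maxima, (evaluable + 6)/0.8, would be 38, 45 and 53 for four, five and six levels.

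**The case against.** The strongest reply is that little depends on these numbers. 9.2 does no statistical testing, 9.4 makes every analysis descriptive, and the 6.3 rules do not use the total sample size. Level 6 may never open, and the maxima are remote. All of that stands, and it limits the weight of the point. It does not make the stated figures agree with the dose table.

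A second reply is that 45 works as a cap: 9.2 presents it as a maximum, the enrolment table repeats it, and entry is by slot reservation (4.3.1). That reading is open. However, the plan does not say what gives way if Part A uses more than 30 places, and under a cap that would be Part B.

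Two stronger readings are tempting and are not supported. A reader might infer that the trial is likely to overrun 45. Under the assumed rates this is a minority outcome, and the expected totals of 44 and 49 hold only if all levels open. A reader might also take 53 and 60 as hard ceilings, or 24 as one for four levels. The step-down path shows that none of them is strict.

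**Conclusion.** Wrong as written. 9.1 and 9.2 do not describe the escalation that the schema, 6.1 and 7.1 provide for. On 9.2's own upward-path arithmetic, 24/30/45 becomes 30/38/53 for levels 1-5 and 36/45/60 for levels 1-6. The expected total becomes about 44 or 49 if all levels open, above the stated likely range of 35 to 42. These figures assume 12 additional patients in Part B and an average 20% inevaluability.

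The chance of passing 45 is about 4 to 18% with six levels and about 2 to 3% with five; it rests on assumed DLT rates and is illustrative only. The escalation rules and the primary endpoint are unaffected. The Part B wording in 9.1 is a separate conflict with 6.1, 6.4 and 9.2. It is a should-fix correction to accrual planning, and nothing here says which set of dose levels is right.

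**What to change.** 1. Reconcile the level count in 9.1 and 9.2 with the schema, 6.1 and 7.1.
2. Restate the expected and maximum evaluable, Part A and overall figures for the reconciled count, with and without level 6, and label them as upward-path planning figures. If the dose table stands and Part B is 12 additional, the maxima are 30/38/53 and 36/45/60.
3. Reconcile the Part B size in 9.1 with 6.1, 6.4 and 9.2.
4. Update the planned enrolment table to match.
5. If 45 is meant as a cap, say so, and say that Part B may be curtailed.

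The cost is wording and one table. No patient is added beyond what the dose table already implies. The downside is that, if the six-level table stands, the stated maximum and expected size become less favourable.

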9.3 Evaluability for DLT, Toxicity, and Response

9.3.1 DLT-Evaluable Population

Each registered patient will be deemed as evaluable for DLT if the patient has received sufficient exposure to the prescribed study treatment and has been observed for the required duration (the DLT-evaluation period), or has experienced a DLT once initiating the study treatment. To meet criteria for sufficient exposure, a patient must have received during the DLT-evaluation period (*i.e.*, Cycle 1):

- at least 4 of 5 planned doses of belinostat; and
- at least 2 of 3 planned doses of MLN4924 (pevonedistat)

Patients who for any reason are not evaluable for DLT will be replaced.

9.3.2 Safety-Evaluable Population

Each registered patient will be deemed evaluable for toxicity (AE evaluation) if the patient has received any study treatment.

9.3.3 Response-Evaluable Population

Response-evaluable patients are those who have received any doses of belinostat or MLN4924 (pevonedistat) and have had at least one post-treatment response evaluation. For response evaluation, the patients are coded as having a response or not having a response as follows:

- Responders - Those patients whose best response assessment is a CR, CRi, CRc, CRm, ML-FS, or PR.
- Non-Responders - Those patients whose best response assessment is SD, morphologic relapse, or progression, or those patients who were not assessed or who were not evaluable.

The coding of patients as responders or non-responders will be made by the PI with the concurrence of the biostatistician.

9.4 Statistical Analysis

All statistical analyses will be descriptive in nature for this phase 1 study.

9.4.1 Statistical Analysis for Primary Objective

Patients' treatment dosing level, dose modification, DLTs, and evaluability for DLTs will be listed and summarized by basic descriptive statistics (such as frequency and proportion). The RP2D will be found based on the criteria defined in Section 6.

9.4.2 Statistical Analyses for Secondary Objectives

Toxicities: AEs and SAEs, dosing levels, treatment received, best clinical response, and demographics will be listed. Basic descriptive statistics will be used to summarize toxicities related to the study drugs by grade, and all toxicities, whether related or unrelated to the study drugs.

Anti-tumor activity: For the response rate calculations, all study reports will contain at least a section with all enrolled patients. Other sections of the reports may detail the response rate for response-evaluable patients only. All response rate analyses based on a subset of patients will be accompanied by explanations of which patients were excluded and the reasons; 95% confidence limits will be given. For patients who do not have disease progression or have not died at time of analysis, the last date the patient was known to be alive and progression free will be used for duration of response analysis. If there are at least 3 responses, duration of response and time to response will be summarized by the first, second, and third quantiles and illustrated by a Kaplan-Meier plot.

PK interactions: PK parameters in MLN4924 (pevonedistat) and in belinostat will be calculated using standard non-compartmental methods and summarized as geometric mean and geometric coefficient of variation. C_{max} and the times needed to reach these concentrations (t_{max}) will be assessed by inspection of the concentration versus time plots. The AUC will be calculated from time zero to infinity ($AUC_{0-\infty}$). V_d and $t_{1/2}$ will also be calculated accordingly. To discover any potential PK interactions between the 2 agents, each PK parameter will be compared with each referenced PK parameter for those who receive single-agent at the same amount dose by a one-sample t-test. The normality of the PK parameters will be checked, and data transformation may be performed if data are highly skewed.

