6.7 Discontinuation of Protocol Therapy

Study treatment may continue until one of the following criteria applies:

- Disease progression. Note: Patients with progressive disease may remain on the study, after discussion with principal investigator, if it is judged that they are deriving a clinical benefit from doing so.
- Toxicity requiring that initiation of a new cycle must be delayed >14 days, unless the delay is due to reasons other than toxicity and has been approved by the study principal investigator.
- Toxicity requiring permanent discontinuation of one of the study drugs.
- Intercurrent illness that prevents further administration of treatment.
- Unacceptable AEs.
- Achievement of complete remission followed by the administration of 3-4 additional cycles of study treatment as “consolidation”.
- Stem cell transplantation.
- Pregnancy
 - All women of child bearing potential should be instructed to contact the investigator immediately if they suspect they might be pregnant (*e.g.*, missed or late menstrual period) at any time during study participation.
 - The investigator must immediately notify CTEP in the event of a confirmed pregnancy in a patient participating in the study.
- Patient decides to withdraw from study treatment.
- Determination by the investigator that discontinuation is in the patient’s best medical interest.
- Termination of the study by sponsor.
- The drug manufacturer can no longer provide the study agent.
- Patient non-compliance that, in the opinion of the investigator, warrants study treatment discontinuation.
- Patient meets criteria for permanent discontinuation of either study agent.
- Subsequent anti-cancer therapy.

Discontinuation of study treatment does not constitute removal from study. Patients who stop study treatment prematurely transition directly into follow-up per Section 6.6. A patient may be removed from study follow-up and be taken off study for any of the following reasons:

- If in the opinion of the treating physician or principal investigator, it is in the best interest of the patient to do so.
- Patient’s decision to discontinue from study follow-up.
- Study sponsor’s decision to discontinue the study.

The reason(s) for protocol therapy discontinuation, the reason(s) for study removal, and the corresponding dates must be documented in the Case Report Form (CRF).

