6.8 Duration of Follow Up

Patients who go off treatment, regardless of response status, remain in follow-up status for a safety follow-up period of 30 days after the last dose of study agent(s) to capture resolution or stabilization of any ongoing treatment-related AEs, and for capture of any evolving AEs. This safety follow-up period may be truncated if the patient begins any subsequent anticancer therapy that would interfere with assessment of treatment-related AEs during the safety follow-up time period. The safety follow-up period may be extended beyond 30 days if felt necessary to evaluate ongoing treatment-related AEs that have not resolved or stabilized.

After the AE assessment safety follow-up period ends, patients who discontinued treatment with a CR, CRi, CRc, CRm, morphologic leukemia-free state (ML-FS), PR or SD will enter a long-term follow-up period to capture reported clinical status for 2 years or until death, at which time they are taken off study. During this extended follow-up reported clinical status will be monitored by review of clinical documentation or by patient contact approximately every 2 months.

Patients who elect to discontinue follow-up may do so and will be taken off study at that time.

Please refer to Section 11 for the study calendar.

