peripheral blood or $\geq 5\%$ blasts in the bone marrow not attributable to any other cause (*e.g.*, bone marrow regeneration). Relapse from PR is defined as $\geq 25\%$ bone marrow blasts not attributable to bone marrow regeneration or use of colony stimulating factors. The appearance of new dysplastic changes should also be considered relapse.

Progressive Disease: Any of the following in patients who have not previously met CR, CRi, CRc, CRm, ML-FS, or PR criteria while on study therapy:

- $\geq 50\%$ increase in the bone marrow blasts (by aspirate differential count) over the best previous assessment (comparing to a minimum bone marrow blast percentage threshold of 20% at baseline or during study at such time as that threshold is met).
- $\geq 50\%$ increase in peripheral blood absolute blast count over the best previous assessment (comparing to a minimum peripheral blood absolute blast count threshold of $\geq 1000/\text{mL}$ at baseline or during study at such time as that threshold is met). In some cases, the peripheral blood absolute blast count may not accurately reflect disease burden, especially with targeted therapies. At investigator discretion, the patient can continue on study with close monitoring of peripheral blood absolute blast count and bone marrow biopsies to assess bone marrow blast percentage (by aspirate differential count) as clinically indicated.
- Development of new extramedullary disease.

Appearance of new dysplastic changes should be closely monitored for emerging relapse. In a patient who has been recently treated, dysplasia or a transient increase in blasts may reflect a chemotherapy effect and recovery of hematopoiesis. Cytogenetics should be tested to distinguish true relapse from therapy-related MDS/AML.

Duration of remission is defined only for patients who achieve CR, CRi, CRc, or CRm and is measured by the interval from the date of CR (by blood count recovery and BM examination), until the date of relapse.

Cytogenetic responses: For patients with AML or MDS, a complete cytogenetic response requires the disappearance of a previously present cytogenetic abnormality (without appearance of new ones), while a partial cytogenetic response requires a $\geq 50\%$ reduction in the number of metaphases positive for the chromosomal abnormality by conventional karyotyping.

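### Duration of response keeps running after transplant or new anticancer therapy, so remission time held by later treatment counts towards the combination

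*Combined protocol and SAP*

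**What the plan says.** - **Definition (9.1):** "Duration of response defined as the time from documentation of tumor response to disease progression or death, whichever occurs first".
- **Censoring (9.4.2):** for patients without progression or death, "the last date the patient was known to be alive and progression free will be used for duration of response analysis". No other censoring rule is given. With at least three responses, quartiles and a Kaplan-Meier plot are reported.
- **Leaving treatment (6.7):** the reasons to stop include "Stem cell transplantation" and "Subsequent anti-cancer therapy". The same section adds: "Discontinuation of study treatment does not constitute removal from study".
- **Follow-up (6.8):** patients who stopped treatment with any response category or stable disease "will enter a long-term follow-up period to capture reported clinical status for 2 years or until death". Footnote e of the Section 11 calendar instead ends this follow-up at progression or death.
- **Responders (9.3.3):** "Those patients whose best response assessment is a CR, CRi, CRc, CRm, ML-FS, or PR". No end date or treatment window is attached.
- **A second duration (12.1):** "Duration of remission is defined only for patients who achieve CR, CRi, CRc, or CRm". It runs to relapse and does not mention transplant or new therapy either.

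The one place where new therapy cuts off observation is the 30-day safety follow-up in 6.8, which may be shortened if the new treatment would confuse adverse event attribution.

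**The concern.** Objective 1.2.2 is to observe the anti-tumor activity of this regimen. A responder who goes on to transplant or another drug stays under observation, and the months in remission that follow are added to duration of response. Nothing in 9.1, 9.4.2 or 12.1 treats the change of treatment as an event or a censoring point, or asks for a second analysis. Section 6.6 expects that some patients in remission will go to transplant, so the path is foreseen. The safety text shows that the authors saw the same confounding for adverse events; the efficacy text has no counterpart.

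At stake is how the duration figures are read. Quartiles may rest on as few as three responders, so one or two patients carried by later treatment could shape the reported median or upper quartile. A reader could not tell the activity of the combination from the effect of what came next.

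**Working it through.** **1. Does the text count the time?** Follow a responder who stops for transplant. Section 6.7 ends treatment and keeps the patient on study. Section 6.8 follows the patient because treatment ended in response. Section 9.1 finds no event without progression or death. Section 9.4.2 then censors at the last date known alive and progression free, which reported clinical status can supply. The interval after transplant is included. The same steps apply to new drug therapy started while still in response.

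**2. Does the text count a later-line response?** Section 9.3.3 sets no window, so it does not forbid it. But disease assessment is scheduled only every two cycles (Sections 11 and 12), extended follow-up collects reported clinical status only, and patients who stop with progression are not listed for long-term follow-up. The remaining path is a patient who left with stable disease and whose records later report a remission.

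**3. What figures does the plan give?** None for response rate, duration or transplant rate. The enrollment figures reproduce: 24/0.8 = 30 in Part A, 12/0.8 = 15 in expansion, 30 + 15 = 45 at most, with 35 to 42 thought likely. Everything below is illustration on stated assumptions.

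**4. Number of responders (assumed).** Section 2.2.1.2 reports 1 CR and 2 PRs among 22 evaluable patients on belinostat plus bortezomib, a different combination. Applying 3/22 gives 35 × 3/22 = 4.8, 38 × 3/22 = 5.2 and 42 × 3/22 = 5.7: about five.

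**5. Five-responder example (durations assumed, in months from response).** Three relapse at 2, 4 and 6. One is transplanted at 2.5 and one starts new therapy at 3; both are event-free to 24. A quartile is the first time the Kaplan-Meier estimate S is at or below 0.75, 0.50 or 0.25.

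- As written (2, 4, 6, 24+, 24+): S(2) = 4/5 = 0.80; S(4) = 0.80 × 3/4 = 0.60; S(6) = 0.60 × 2/3 = 0.40. First quartile 4, median 6, third quartile not reached.
- Censored at the change (2, 2.5+, 3+, 4, 6): S(2) = 0.80; S(4) = 0.80 × 1/2 = 0.40; S(6) = 0. First quartile 4, median 4, third quartile 6.

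Censoring at the last assessment before the change gives the same result if both assessments fall after month 2.

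Now drop the new-therapy patient, leaving one transplant among four responders:

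- As written (2, 4, 6, 24+): S = 0.75, 0.50, 0.25; quartiles 2, 4, 6.
- Censored (2, 2.5+, 4, 6): S = 0.75, then 0.75 × 1/2 = 0.375, then 0; quartiles 2, 4, 6.

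Here one patient moves no quartile.

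**6. Larger-sample illustration (assumed).** Let duration on the regimen be exponential with median m. At 2 months a share f of those still in response go to transplant, with median M from then on. For t > 2, S(t) = 2^(−2/m) × [f × 2^(−(t−2)/M) + (1−f) × 2^(−(t−2)/m)]. Non-informative censoring at transplant recovers m. Medians without it:

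| m | f | M = 12 | M = 24 |
|---|---|---|---|
| 4 | 10% | 4.2 | 4.2 |
| 4 | 25% | 4.5 | 4.6 |
| 4 | 50% | 5.1 | 5.8 |
| 6 | 10% | 6.2 | 6.4 |
| 6 | 25% | 6.6 | 7.1 |
| 6 | 50% | 7.5 | 9.0 |
| 8.3 | 10% | 8.5 | 8.8 |
| 8.3 | 25% | 8.9 | 9.8 |
| 8.3 | 50% | 9.5 | 12.0 |

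The increase runs from 4.2 − 4 = 0.2 to 12.0 − 8.3 = 3.7 months. The 8.3 is the median reported for pevonedistat plus azacitidine in Section 2.2.2.2; the other inputs are chosen.

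**7. Response rate, if one later-line remission were counted.** 3/45 = 6.7% (exact 95% limits 1.4 to 18.3) would become 4/45 = 8.9% (2.5 to 21.2). In a cohort of 12, 3/12 = 25.0% (5.5 to 57.2) would become 4/12 = 33.3% (9.9 to 65.1).

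**The case against.** The strongest reply is that following response to progression or death whatever treatment comes later is a coherent, treatment-policy measure, and that censoring at transplant has its own bias because patients chosen for transplant differ from the rest. Both points stand. They argue for keeping the present analysis, not for showing it alone: it describes the course after starting the regimen, while the stated objective concerns activity of the regimen.

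Frequency is a second reply. Exclusion 3.2.15 removes current candidates for potentially curative allogeneic transplant unless they declined, and the documents give no transplant rate. That limits the transplant path. It does not close it, since 6.6 and 6.7 provide for transplant after entry, and it does not touch subsequent drug therapy.

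Third, a reader might infer that remissions produced by later treatment will be counted as responses and will raise the response rate. The documents do not support that. Assessments follow the cycles, most response categories need marrow findings that extended follow-up does not schedule, Section 12.1 ties its progression definition to response achieved on study therapy, and 9.3.3 leaves coding to the principal investigator with the biostatistician's concurrence. What remains is a missing window.

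A reader might also take a long remission after transplant as a completed long response. It is not: the patient is censored, and the clock starts at documentation of response, not at transplant. Nor can response rate and duration be called the only activity measures. Time to response and cytogenetic response are also defined, and one secondary objective and one secondary endpoint are redacted.

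**Conclusion.** The point holds for duration of response: under the stated rules, remission time after transplant or new anticancer therapy is included, with no analysis that separates it. For response rate it holds only as an unstated window that could, but need not, admit a later-line remission in a patient who left with stable disease; the risk is small.

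The size is unknown. Two patients out of five shifted the median by 2 months and made the third quartile unreachable in the example; one out of four shifted nothing. The larger model gives 0.2 to 3.7 months. These results depend on assumed durations, on the assumed share leaving in response, and in the model on non-informative censoring. The documents cannot show which case is closer.

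This is a minor point and a cheap improvement. The endpoint is secondary, all analyses are descriptive (9.4), and the recommended phase 2 dose, the safety analyses and the sample size are unaffected.

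**What to change.** 1. **Section 9.4.2:** report duration of response two ways from the same patients: as now, and censored at the last assessment before the first transplant or subsequent anticancer therapy. Mark the dates of those events on the Kaplan-Meier plot.
2. **Section 9.3.3:** limit best response to assessments made before those events.
3. **Data collection:** add a follow-up field for the date of transplant or first new therapy. Section 6.7 requires dates and reasons for stopping treatment, which captures these events only when they are the reason for stopping; one that begins later in follow-up has no stated field.
4. **Sections 6.8 and 11:** reconcile the end of extended follow-up, which is 2 years or death in one and includes progression in the other.

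The cost is a few sentences, one extra curve and one date field. The downside is that the censored version is open to informative censoring, which is why both versions should be shown.
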